1.4 Rationale for allowing 3 different APBI techniques

Prospectively conducted clinical trials have demonstrated the safety and efficacy of each of the APBI techniques that will be allowed on this study. On the recently closed NSABP B-39/RTOG 0413 protocol, A Randomized Phase III study of Conventional Whole Breast Irradiation Versus Partial Breast Irradiation for Women with Stage 0, I, or II Breast Cancer, APBI could be administered with brachytherapy or 3D-CRT at the physician's discretion, highlighting the equipoise that exists between the techniques and justifying pooling outcomes of patients treated with either technique on this study to assess the primary and secondary endpoints. Given the conformal and homogeneous dose distribution of protons as well as the favorable outcomes reported to date, proton APBI will also be allowed at centers where this modality is available. At least one of the three APBI techniques allowed in this study is available at all participating centers. Similar to NSABP-B-39/RTOG 0413, the APBI technique to be utilized will be at the physician's discretion and will be based on technical considerations, availability at the radiation oncology facility, insurance coverage considerations, and patient preference. In addition, after reduction mammoplasty patients will only be allowed if they undergo brachytherapy as the extensive manipulation of breast tissue at the time of surgery is felt to preclude reliable targeting with external beam photon or proton techniques.

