2.0 Goals

2.1 Primary:

- 2.11 To evaluate the rate of adverse cosmesis (defined as fair or poor cosmesis) with accelerated 3 fraction APBI at 3 years, compared to baseline.

2.2 Secondary:

- 2.21 To evaluate the acute and late toxicities of accelerated 3 fraction APBI
- 2.22 To evaluate local disease control of accelerated 3 fraction APBI.
- 2.23 To assess the rate of patient reported adverse cosmesis at 2 years, compared to baseline

- 2.23 To assess quality of life and other patient reported outcomes following accelerated 3 fraction APBI
- 2.24 To compare the local control, acute and late toxicities, cosmesis, quality of life and other patient reported outcomes between the three radiation therapy techniques (3D-CRT, proton, brachytherapy).
- 2.24 To evaluate clinical features, dose-volume parameters, and genetic variants associated with fair and poor cosmetic outcome

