5.0 Stratification Factors

- None – Patients, along with their physicians, will determine which treatment arm is appropriate for their needs. The APBI technique to be utilized will be based on technical considerations, availability at the radiation oncology facility, insurance coverage considerations, and patient preference. In addition, after reduction mammoplasty patients will only be allowed if they undergo brachytherapy as the extensive manipulation of breast tissue at the time of surgery is felt to preclude reliable targeting with external beam photon or proton techniques.

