6.0 Randomization/Registration Procedures

6.1 Randomization-none

6.2 Registration Procedures

Registration will entail confirming patient eligibility and signing the informed consent

6.21 Pretreatment tests/procedures, (see Section 4.0) will be completed within the guidelines specified on the assessment schedule.

6.22 All required baseline symptoms (see Section 10.0) must be documented and graded.

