16.67 *Distant recurrence incidence*: The distant breast cancer recurrence cumulative incidence will be estimated using a competing risks method (Gooley et al.). The competing risks will be local/regional breast cancer recurrence and death.

16.68 *Disease-free survival*: DFS is defined as the time from registration until the time of disease recurrence or death due to any cause. The DFS will be estimated with a Kaplan-Meier estimator and curve. Estimates will be given for specific time points along with 95% CIs.

16.69 *Overall survival*: The OS will be estimated with a Kaplan-Meier estimator and curve. Estimates will be given for specific time points along with 95% CIs.

16.7 Exploratory Analyses: Exploratory comparisons of the local control, acute and late adverse events, quality of life, and cosmesis among the three radiation regimens will be made. Comparisons of categorical variables will be done with a chi-square test or Fisher's exact test, whichever is appropriate. Comparisons of continuous variables will be done with an ANOVA or Kruskal-Wallis test, whichever is appropriate. Measurements over time (i.e. QOL) will be summarized as area under the curve (AUC) and these values will be analyzed as continuous outcomes. All tests will be two-sided and a p-value less than 0.05 will be considered significant. No adjustments will be made for multiple comparisons.

Correlative Science: Adverse cosmesis has been reported to be significantly increased in prior studies of APBI, yet predictors of adverse cosmesis are poorly understood.^{47,48} If a subset of patients at high risk of complications could be identified, their treatment could be personalized or they could be counseled to pursue other therapeutic options altogether. In the setting of WBI, factors previously reported to be associated with worsened cosmesis include inferior tumor location, large excision volume, the presence of postoperative breast complications, higher dose (including radiotherapy boost), inhomogeneity, and use of concurrent chemotherapy.⁵⁷⁻⁵⁹ In order to begin identifying predictive factors for fair and poor cosmesis following 3 fraction APBI we will analyze clinical and dose volume parameters correlated with increased risk.

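### Section 16.7 compares three non-randomised techniques on cosmesis without baseline adjustment, so a baseline imbalance can appear as, or hide, a technique effect

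*Combined protocol and SAP*

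**What the plan says.** Section 2.2 lists among the secondary goals (the first item numbered 2.24) "To compare the local control, acute and late toxicities, cosmesis, quality of life and other patient reported outcomes between the three radiation therapy techniques". Section 16.7 takes this up: "Exploratory comparisons of the local control, acute and late adverse events, quality of life, and cosmesis among the three radiation regimens will be made". For cosmesis as a fair-or-poor outcome the method is "Comparisons of categorical variables will be done with a chi-square test or Fisher's exact test, whichever is appropriate". Continuous outcomes get ANOVA or Kruskal-Wallis. The threshold is "All tests will be two-sided and a p-value less than 0.05 will be considered significant", and "No adjustments will be made for multiple comparisons".

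The groups are self-selected. Section 6 states "6.1 Randomization-none", and section 5.0 states "None – Patients, along with their physicians, will determine which treatment arm is appropriate for their needs". Availability, insurance and technical considerations also enter the choice. One difference is built in: "after reduction mammoplasty patients will only be allowed if they undergo brachytherapy" (sections 1.4 and 5.0, with exclusion 3.48).

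The section 4.0 schedule includes a cosmesis assessment at baseline. Sections 16.5 and 16.64 express cosmesis as a difference between 3 years and baseline. Section 16.43 checks grade 3 toxicity, IBTR, race, chemotherapy, age and tumor size across techniques to decide on pooling. It does not check baseline cosmesis.

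**The concern.** Without randomisation, women in the three groups may start with different cosmesis. If adverse baseline status tends to persist, a group that starts worse also ends worse, and a raw comparison of 3-year rates credits that to the technique. An imbalance in the other direction can mask a real difference. The plan has the one covariate most directly tied to the outcome but does not use it here. No regression, stratified test or propensity method is specified for any technique comparison.

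Section 16.7 also leaves open whether cosmesis means 3-year status or change from baseline. The choice matters, because the two analyses go wrong under different conditions. At stake is how far a p-value below 0.05 between photon, proton and brachytherapy can be believed when goal 2.24 is reported.

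**Working it through.** **The plan's own figure.** Section 16.7 gives none for these comparisons. The overall sample size in 16.41 does reproduce: 1.645² × 0.10 × 0.90 / 0.04² = 152.2, rounded up to 153. Equal groups give 153 / 3 = 51 per technique, within the planned 40 to 60.

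**Inputs.** Adverse cosmesis of 19% at baseline and 29% at 3 years comes from the APBI arm of the randomised trial cited in section 1.3.2. The 10-point rise matches 16.42. Baseline rates by technique, and the share of women with adverse baseline cosmesis who recover (r), are assumptions and are varied.

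**Model with no technique effect.** Every woman has the same chances given her baseline status. The chance w of worsening from a good baseline is set so that the net rise is 10 points at a 19% baseline: 0.81w − 0.19r = 0.10.
- r = 0: w = 0.100 / 0.81 = 0.123
- r = 0.3: w = 0.157 / 0.81 = 0.194
- r = 0.6: w = 0.214 / 0.81 = 0.264

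**Why persistence decides the answer.** The expected 3-year rate in a group with baseline b is b(1 − r) + (1 − b)w. For baselines 9/19/29%:
- r = 0 gives about 20/29/38% at 3 years. The imbalance carries through, while changes are nearly equal (about 11, 10 and 9 points).
- r = 0.6 gives about 28/29/30%. The imbalance almost vanishes from 3-year status, but changes are about 19, 10 and 1 points.

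**False-positive rates** (3,000 simulated trials per row, 51 per technique, two-sided 0.05):

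| Baseline adverse, three groups | r | Chi-square, 3-year status | ANOVA, change | Mantel-Haenszel, stratified by baseline |
|---|---|---|---|---|
| 19/19/19% | 0 | 4.7% | 4.8% | 4.6% |
| 14/19/24% | 0 | 12.6% | 5.1% | 4.6% |
| 14/19/24% | 0.3 | 7.6% | 6.6% | 5.3% |
| 14/19/24% | 0.6 | 5.2% | 8.7% | 5.0% |
| 9/19/29% | 0 | 39.8% | 5.7% | 4.4% |
| 9/19/29% | 0.3 | 15.9% | 14.5% | 5.0% |
| 9/19/29% | 0.6 | 6.1% | 25.6% | 4.9% |

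An extreme spread of 5/19/33% gives 70.0%, 28.2% and 6.1% for chi-square at the three values of r, against 4.5% to 5.0% stratified. Unequal groups of 40/53/60 at 9/19/29% and r = 0.3 give 15.4% against 4.7%.

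**A second model.** With 56 per technique (168 / 3), 17% of good-baseline and 80% of adverse-baseline women are adverse at 3 years. This gives 0.81 × 0.17 + 0.19 × 0.80 = 0.29 overall. At 10/19/28%, chi-square rejects 19.3% and baseline-adjusted logistic regression 5.9%. At 5/19/19% the figures are 17.3% and 5.5%.

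**When adjustment itself fails.** Keep the second model and give all groups the same true post-surgical baseline of 19%. Let one group's recorded baseline be lower only because it was taken before surgery. With recorded baselines 5/19/19%, chi-square rejects 4.6% and the adjusted logistic regression 19.8%. With 0/19/19% the figures are 4.6% and 32.7%. A repeat gave about 17% to 31% for the adjusted test and 5% to 6% for chi-square.

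**The case against.** The strongest defence is that these comparisons are labelled exploratory in 16.3 and 16.7, and no decision rule uses them. Section 16.43 screens several baseline factors, cosmesis is elsewhere analysed relative to baseline, and adjustment can do harm if baselines are not comparable.

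Much of this stands. Exploratory status limits the consequences, though it does not make an avoidably confounded p-value informative. The 16.43 screen governs pooling only, omits baseline cosmesis and adjusts nothing. Expressing cosmesis as change is not a remedy either, since the change score reaches 25.6% in the table. The point about harm is sound and shapes the fix.

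Four stronger readings are tempting, and the documents support none of them.
- **That baseline differences will appear as technique effects.** They can. It takes a real imbalance and, for 3-year status, persistence of adverse baseline cosmesis.
- **That 16.7 certainly compares raw 3-year rates.** The outcome is not stated.
- **That this comparison becomes the main result if pooling fails.** Section 16.43 then calls for separate reporting of each arm, as secondary and exploratory endpoints. It does not promote the between-technique test.
- **That baseline timing differs by technique.** The schedule defines baseline for everyone as before radiation. The footnote allowing photographs before surgery or only before radiation draws no distinction by technique. A difference is plausible, because brachytherapy patients consult preoperatively and the device goes in at surgery (7.12), while external-beam patients may first consent afterwards (7.11, 7.13). That remains an inference.

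**Conclusion.** The concern holds in a limited form. Section 16.7 plans unadjusted comparisons of self-selected groups, leaves the cosmesis outcome undefined and does not use a baseline that is collected. Within these exploratory comparisons, a baseline imbalance can pass for a technique effect or conceal one.

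The size depends on assumptions that the documents cannot settle. The 3-year chi-square false-positive rate is about 5-6% with balanced baselines or when most adverse baselines recover. It is about 15-40% at spreads such as 10/19/28% or 9/19/29% with baseline status largely persisting. A baseline-adjusted test stays near 5% across these scenarios if baseline means the same thing in every group. If it does not, the adjusted test can be the worse of the two, at about 17% to 33%. The primary pooled analysis and its decision rule are not affected.

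**What to change.** In section 16.7:
1. Name 3-year adverse cosmesis as the outcome for the technique comparison.
2. Compare techniques by logistic regression (penalised if sparse) or a Mantel-Haenszel test, adjusted for baseline cosmesis. Add a few prespecified factors as events allow: age, tumor size, and cosmesis-related factors that 16.7 itself names, such as tumor location and chemotherapy. If 29% are adverse at 3 years, 0.29 × 153 gives about 44 events, so the list must be short.
3. Record whether each baseline assessment was made before or after surgery. Repeat the analysis among patients with comparable timing.
4. Repeat it without reduction-mammoplasty patients. They occur only in the brachytherapy group, so no model can separate that factor from technique.
5. Report estimates with confidence intervals, and keep the unadjusted tests alongside.
6. Label all technique comparisons, including toxicity, as non-randomised and exploratory.

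The cost is a few sentences, one recorded item on timing and a little more analysis. Sample size, treatment and the primary endpoint do not change. Estimates may be unstable if events are few, and residual confounding will remain.

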If the increase in APBI adverse cosmesis rate from baseline is 5.0%, there is a 98.4% chance of concluding that the APBI adverse cosmesis increase from baseline is acceptable; this drops to 72.8% if the true rate is 10%, and further drops to 49.6% if the true rate is 15%. If the increase in APBI adverse cosmesis rate from baseline at 3 years is 20% or greater, we are most likely to recommend no further investigations, and conclude that the increase in APBI adverse cosmesis rate is unacceptably high.

Other considerations: Adverse events, quality/duration of response, and patterns of treatment failure observed in this study, as well as scientific discoveries or changes in standard care will be taken into account in any decision to terminate the study.

16.43 Preliminary Analysis: The preliminary analysis is to examine whether the data from the three methods (photon, proton and brachytherapy PBI) can be combined by assessing any difference in the safety profile and baseline patient and tumor characteristics. We will conclude that the variability in the three samples is acceptable and proceed to the primary analysis if all the following conditions are met:

- The difference in rate of grade 3 toxicity between the groups is $\leq 10\%$.
- There is not a significant difference in the rate of IBTR between the groups (using pair-wise chi-squared tests with Bonferroni correction for multiple comparisons).
- The distribution of African Americans and the percentage of cytotoxic chemotherapy use between the groups is not significantly different (using pair-wise chi-squared tests with Bonferroni correction for multiple comparisons).
- The distribution of age between the groups is not significantly different (p -value ≥ 0.05 using a Tukey's test). The difference in age in 10 increments (50-59, 60-69, and ≤ 70) will be reported.
- Tumor size will be dichotomized to two categories ($\leq 1\text{cm}$ vs $1\text{-}2\text{cm}$). The percentage of larger tumor ($1\text{-}2\text{cm}$) between the groups is not significantly different (using pair-wise chi-squared tests with Bonferroni correction).

If any of the above conditions are failed to be met, we will only report the safety and efficacy of each individual arm as secondary and exploratory endpoints.

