16.44 Accrual time and Study duration: Since 10/1/2012 patients have been treated with brachytherapy APBI using an 8 or 10 fraction regimen and prospectively followed as part of a clinical registry at the Mayo Clinic in Rochester, MN. Patient interest in the procedure has steadily increased, and in the last 3 months, 13 patients have been treated (median 4.3 patients per month), all of whom would be eligible for this study. A similar to increased level of accrual of brachytherapy patients is anticipated during the course of this study as familiarity with this procedure amongst surgical and radiation oncology providers rises. With the addition of the photon APBI alternative for patients, we anticipate an accrual rate of 5 patients per month for the first year until the opening of

the Mayo proton facility, after which an accrual of 8 patients per month is anticipated. Therefore, the accrual period for this study is expected to be approximately 3 years. We plan to open this study at the Mayo Clinic in Scottsdale and Jacksonville which will further enhance accrual. Final analysis may begin approximately 5 years after the trial begins, i.e. as soon as the last patient registered has been observed for at least 24 months. A maximum of 60 patients and a minimum of 40 patients will be enrolled per treatment arm.

16.5 **Primary Analysis:** The primary analysis will be to estimate the percentage difference in patients with adverse cosmesis (fair or poor cosmesis) at 3 years compared to baseline. All patients meeting the eligibility criteria who have signed a consent form and started treatment will be in the primary analysis. The percentage difference in patients with adverse cosmesis will be estimated using a binomial estimator (number of women who had an adverse cosmesis event at 3 years minus number of women who had an adverse cosmesis event at baseline, and then divided by total number of women in the primary analysis) and a 95% exact binomial confidence interval. As mentioned above, the following decisions will be made based on the 95% CI:

- ***The upper bound of the 95% CI lies below 14%:*** APBI adverse cosmesis is acceptable.
- ***The upper bound of the 95% CI lies above 14%:*** No evidence to show that APBI adverse cosmesis is acceptable.

16.6 **Secondary Analyses**

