16.61 *Acute adverse events (up to 90 days post-RT):* All patients who were registered to the study and started treatment will be included in the acute adverse event analysis. An acute adverse event is an AE, regardless of attribution, that occurs up to 90 days post-RT. The maximum grade for each type of acute AE will be recorded for each patient. Data will be summarized as frequencies and relative frequencies. Additionally, the relationship of the adverse event(s) to the study treatment will be taken into consideration.

16.62 *Late adverse events:* All patients who were registered to the study and started treatment will be included in the late adverse event analysis. A late adverse event is an AE, regardless of attribution, that occurs at least 90 days post-RT and up to 3 years post-RT. The maximum grade for each type of late AE will be recorded for each patient. Data will be summarized as frequencies and relative frequencies. Additionally, the relationship of the adverse event(s) to the study treatment will be taken into consideration. Prior APBI reports have suggested rates of grade 3 or 4 toxicity to be $\leq 10\%$.^{18,47,55,56}

16.63 *Quality of life:* The QOL measurements will be summarized at each time point as mean \pm SD and median (minimum value, maximum value). Changes in the QOL measurements from baseline will be determined at each follow-up measurement. These will be displayed as spaghetti plots. The assessment of the changes at each time point will be done with a paired t-test or Wilcoxon signed rank test, whichever is appropriate.

16.64 *Cosmesis*: The values of the cosmesis instruments (patient self-reported and panel-assessed) will be summarized with the frequencies of fair or poor cosmesis events at baseline and 3 years, and the difference at 3 years, as well as their relative exact binomial confidence intervals.

16.65 *IBTR incidence*: The IBTR cumulative incidence will be estimated using a competing risks method (Gooley et al.). The competing risks will be regional/distant breast cancer recurrence and death.

16.66 *Regional recurrence incidence*: The regional breast cancer recurrence cumulative incidence will be estimated using a competing risks method (Gooley et al.). The competing risks will be local/distant breast cancer recurrence and death.

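### IBTR and late toxicity are compared between techniques as crude proportions, while 16.44 allows analysis before every woman has 3 years: a minor bias against techniques that enrol early, cheaply removed

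*Combined protocol and SAP*

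**What the plan says.** **Comparison between techniques.** Section 16.7 states that "Exploratory comparisons of the local control, acute and late adverse events, quality of life, and cosmesis among the three radiation regimens will be made". For categorical outcomes, "Comparisons of categorical variables will be done with a chi-square test or" Fisher's exact test, and "All tests will be two-sided and a p-value less than 0.05 will be considered significant". No test that handles censoring is named. The pooling check in 16.43 requires that "There is not a significant difference in the rate of IBTR between the groups", judged by pair-wise chi-squared tests with Bonferroni correction. It also requires grade 3 toxicity rates to differ by no more than 10 points.

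**Estimation.** Section 16.65 takes a different route: "The IBTR cumulative incidence will be estimated using a competing risks method". For late toxicity, 16.62 says "All patients who were registered to the study and started treatment will be included in the late adverse event analysis". The maximum grade is tabulated as frequencies, with no rule for incomplete follow-up.

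**Windows and timing.** Section 16.3 defines IBTR at 3 years from registration, and 16.62 ends late adverse events at 3 years post-RT. Section 16.44 allows final analysis once the last patient has 24 months, at about 5 years. Section 16.8 sets primary endpoint completion when the last patient has at least 3 years. On accrual, 16.44 expects 5 women a month during year 1, when protons are not yet available. The change it foresees comes with "the Mayo proton facility, after which an accrual of 8 patients per month is anticipated".

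**The concern.** Recurrences and late effects accumulate with time. In a crude proportion, a woman seen for 24 months of a 36-month window fills a whole place in the denominator, and anything that happens to her in the third year is missed. If one technique enrols later than another and the data are cut before everyone has completed the window, the later technique shows a lower rate at identical risk. A woman who stops attending is treated the same way: she is counted as event-free from then on.

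Two uses of the data are exposed. One is goal 2.24, the comparison of techniques. The other is the pooling check in 16.43, where two of the conditions are outcome rates and failing any condition restricts the report to individual arms. The plan already has the right tool for IBTR in 16.65 but does not carry it into the comparisons.

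**Working it through.** **1. The plan's accrual period.** At 16.44's rates, 168 women take 12 + (168 − 60)/8 = 25.5 months, not the stated 3 years or so. The stated figures do agree with each other: 36 + 24 = 60 months, about 5 years. Both timelines are therefore examined.

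**2. Technique mix (assumed).** The rise from 5 to 8 per month is taken to be all proton. Proton then contributes 3 × 13.5 = 40.5 women over months 12 to 25.5. Photon and brachytherapy contribute 60 in year 1 and 5 × 13.5 = 67.5 afterwards, 127.5 in all.

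**3. Follow-up at last patient + 24 months (month 49.5).** Women entering after month 12 have 24 to 37.5 months, spread evenly.
- Reached 3 years: proton 1.5/13.5 = 11%; photon/brachytherapy (60 + 67.5 × 0.111)/127.5 = 53%.
- Mean time observed within the 36-month window: proton (12/13.5) × 30 + (1.5/13.5) × 36 = 30.7 months; photon/brachytherapy (60 × 36 + 67.5 × 30.7)/127.5 = 33.2 months. The ratio is 0.92.

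**4. Share of late toxicity seen.** Assume late effects arise evenly from month 3 to month 36 and are recorded only at the 12-, 24- and 36-month visits (visit schedule in 18.1). A woman between 24 and 36 months has shown (24 − 3)/33 = 0.636 of hers.
- Proton: 0.889 × 0.636 + 0.111 = 68%.
- Photon/brachytherapy: (60 + 67.5 × 0.677)/127.5 = 83%.

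**5. Size, with no true difference between techniques.** Cohorts of 56 are assumed; rejection rates are for the three-group chi-square test at 5%, by simulation.

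| Outcome (true 3-year risk) | Photon/brachytherapy v proton, crude | Gap | Rejection |
|---|---|---|---|
| Late event, 10% | 8.3% v 6.8% | 1.5 points (0.8 of 56 women) | about 5% |
| Late event, 20% | 16.6% v 13.5% | 3.1 points | about 7% |
| Late event, 50% | 41.4% v 33.8% | 7.6 points | about 12% |

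The 10% row corresponds to the upper limit that 16.62 cites for grade 3 or 4 toxicity. The 20% and 50% risks are assumptions for common lower-grade effects; section 8.2 says telangiectasia and pigment changes are common but gives no rate.

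For IBTR, take the 5-year 3.8% from the balloon-applicator registry in 1.2. At constant hazard the 3-year risk is 1 − 0.962^0.6 = 2.3%. The gap is about 2.3 × (33.2 − 30.7)/36 = 0.16 points, or 0.1 of 56 women.

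**6. If brachytherapy fills year 1.** Section 16.44 reports 4.3 brachytherapy patients per month against an expected total of 5. Suppose 52 of 56 brachytherapy women and 8 of 56 photon women enter in year 1.
- Shares of late toxicity seen: brachytherapy (52 + 4 × 0.677)/56 = 98%; photon (8 + 48 × 0.677)/56 = 72%; proton 68%.
- For a 10% event this gives 9.8%, 7.2% and 6.8%. The widest gap is 3.0 points (1.7 women), and rejection is about 7%. At an assumed 50% risk, rejection is roughly one third.
- For IBTR: 2.27% brachytherapy v 1.96% proton, 0.3 points or 0.2 of 56 women.

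**7. Later cut-offs.**
- Month 60 at 16.44's rates: proton 0.889 + 0.111 × 0.636 = 96% seen; the others (60 + 67.5 × 0.96)/127.5 = 98%. Rejection is 4–6%.
- Month 60 if accrual really takes 36 months: this is again last patient + 24. Mean observed time is 33.0 months for proton against 34.0–35.8 for brachytherapy. With continuous observation, the gap is 0.3–0.7 points for a 10% event.
- Last patient + 36 months: no administrative gap.

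**The case against.** A reader might infer that proton, opening a year late, has a year less observation and so will look better. Counting all follow-up at month 49.5 does give means of 36.7 v 30.8 months (ratio 0.84). The documents do not support that reading. IBTR and late adverse events both stop at 3 years, so time beyond 36 months does not count, and the ratio within the window is 0.92. Nor is the effect specific to proton: if brachytherapy takes most year-1 places, photon is nearly as late, and the contrast is brachytherapy looking worse than both.

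It can also be said that the administrative bias comes from the 24-month clause in 16.44, not from the choice of test. If 16.8 governs, every woman has 3 years and that part is zero. The comparisons in 16.7 are labelled exploratory, and technique is chosen by physician and patient, so selection confounding remains under any test. All of this stands, and it is why the point is minor.

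Three things remain. Section 16.8 defines a completion date and does not cancel 16.44's permission to analyse at 24 months. Local control in 16.7 carries no stated horizon, and follow-up runs to 5 years, so the 3-year window should be written in. And waiting does not deal with dropout: under 13.2 and 18.1, women who leave observation move to event monitoring, which collects survival and disease status. Recurrence can still be captured for them, but late toxicity is not, and they stay in its denominator.

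**Conclusion.** The inconsistency is in the text: IBTR is estimated with a method that handles incomplete follow-up and compared with one that does not, and late toxicity is both summarised and compared crudely. At the 24-month cut-off, crude rates are biased downward in later-enrolling techniques.

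The size is small. The expected shift is a fraction of a woman per cohort for IBTR. For a 10% late event it is about one woman, or 1.7 if brachytherapy fills year 1 and effects are seen only at visits. Neither is likely by itself to change the pooling decision; a shift of 1.5 to 3.0 points is well inside the 10-point toxicity margin. The effect is noticeable only for common late effects: rejection of about 7–12% under the main mix, and more if brachytherapy is strongly front-loaded.

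These figures rest on an assumed technique mix, equal cohorts of 56 in the simulation, even accumulation of late effects, and assumed 20% and 50% risks. The accrual split in step 2 does not give equal cohorts, and halving 127.5 gives about 64, above the maximum of 60. With 64/64/40, rejection is about 5–6% at 20% risk and 10–11% at 50%. The administrative part nearly vanishes at month 60 if accrual ends near month 25.5, persists in reduced form if accrual takes 36 months, and is zero once everyone has 3 years. Loss to follow-up remains in every case. Severity: minor.

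**What to change.** - In 16.43 and 16.7, compare IBTR and local control between techniques on the cumulative incidence curves of 16.65, censored at 3 years from registration, using Gray's test or a cause-specific log-rank test. State that local control uses the 16.3 window.
- Compare late adverse events by cumulative incidence of the first event of the chosen grade, censored at the last toxicity assessment, with death as a competing event. Alternatively, compare frequencies only at visits that all cohorts have reached, among women assessed there.
- Keep chi-square and Fisher tests for baseline characteristics and fixed-time outcomes.
- Reconcile 16.44 with 16.8 so that 3-year endpoints are analysed once every patient has 3 years, and correct the accrual period or the rates so that they agree.

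The cost is SAP wording and slightly more programming, with no new data. Analysis may come later than 16.44 now permits. Power between techniques stays low, as it is now.
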